# 8.1.1 Dosage Form, Manufacturing, Packaging, and Labeling

In this protocol, the term study medication refers to all or any of the drugs defined below.

The study sites will be supplied with double-blind study medication containing dexlansoprazole 30 mg capsules or matching placebo blister cards, as shown in Table 8.a.

Study Drugs Dosage Strength/Dosage Form Manufacturer		Manufacturer	
Dexlansoprazole	30 mg capsules	Takeda Pharmaceutical Company Ltd.	
Placebo	capsules (dose is not applicable) Takeda Pharmaceutical Company Ltd.		

Table 8.aStudy Drugs

The study sites will be supplied with study medication that is blinded via over encapsulation (OE) of dexlansoprazole 30 mg capsules and placebo. The study drug will be foil/foil blistered and packaged in 7-day child resistant blister cards containing 7 OE capsules. Each card will have a single-panel multilingual label that will contain, but will not be limited to: protocol number, medication identification (ID) number, name and strength of the product, quantity of dosage unit, directions for use, storage conditions, country specific regulatory caution statement, and name and address of the sponsor. The matching placebo capsules will be manufactured by Takeda Pharmaceutical Company Ltd. The study medication is overencapsulated, foil/foil blistered, packaged, labeled and distributed by Fisher Clinical Services.

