# 8.1.3 Dose and Regimen

Once a subject meets all inclusion criteria and none of the exclusion criteria, the site will randomize the subject on Study Day -1 via the IWRS, which will assign a study drug kit number. The study drug kit number will encode the subject's randomization to 1 of the 2 arms (dexlansoprazole 30 mg capsules QD or placebo QD) of the study at a ratio of 1:1, according to the randomization schedules generated prior to study start.

Subjects will receive three 7-day cards on Study Day -1 and Week 2. All subjects will self-administer 1 dexlansoprazole capsule QD or placebo QD at approximately the same time each morning without regard to food. The dose of study drug will be taken with a sip of water on the day of the fasting lab visit. Subjects should continue taking study drug so that the last dose is taken in the morning of the day before the Final Visit (Visit 4).

Investigational Product	Formulation	Dosage	Mode of Administration	Manufacturer and Location
Dexlansoprazole	30 mg capsule	30 mg QD AM	Oral	Takeda Pharmaceutical Company Ltd.
Placebo	0 mg capsule	0 mg QD AM	Oral	Takeda Pharmaceutical Company Ltd.

Table 8.cSponsor-Supplied Drug

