5.2.3 Handling of Missing/Partial Date

Completely missing start or end dates remained missing, with no imputation applied.

Partial dates were imputed using the below conventions:

- If the partial date was a start date and:
 - If only missing day, then impute as the first day of the month.
 - If missing both month and day then, impute as the first day of the year.
- If the partial date was an end date and:
 - If only missing day, then impute as the last day of the month.
 - If missing both month and day, impute as the last day of the year.

- If the partial date was in the same month (only missing day) or same year (missing both month and day) as the study treatment, and the imputed start date of an adverse event (not pretreatment event) was prior to the start of study treatment, then the start date of study treatment was assumed to be the start date. The AE would then be considered as start on treatment (worst case scenario).
- If the imputed end date was after the subject’s last visit date (or last contact date), then the last visit date (or last contact date), was considered as the end date.

The recorded partial date was displayed in the listings.

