5.9 Study Drug Exposure and Overdose

Overall study drug compliance (%) was determined as (total count of capsules taken / total number of days on study drug) \times 100%. The total number of days on study drug (exposure) was

calculated as date of last dose of study drug - date of first dose of study drug + 1, assuming no gaps in the dosing interval. Any gaps in dosing interval was ignored in the calculation of the total. If last dose date was missing, then 35 days were imputed as treatment period. Summary statistics for the total number of days on study drug and overall compliance were generated for the safety analysis set.

The number and percentage of subjects with overall study drug compliance of <80%, 80-<90%, and ≥90% was also summarized for the safety analysis set. Subjects with unreturned study drug were assumed to have taken 1 capsule of study drug for each day of exposure for the calculation of overall compliance. Subjects with overall compliance ≥100% were set to 100% in the analysis.

In addition, diary compliance was determined as the percentage of days during treatment with two diary entries:

$$\text{Diary Compliance} = \frac{\text{(Number of days with two diary entries collected during treatment period)}}{\text{(Number of days with two diary entries expected during treatment period)}} \times 100\%$$

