5.10.1 Primary Efficacy Endpoint

The percentage of days with neither daytime nor nighttime heartburn over the 4 weeks of treatment was summarized descriptively. Comparisons between dexlansoprazole capsules and placebo was made using a Wilcoxon rank-sum test. The two-sided p-value was presented for the difference between dexlansoprazole capsules and placebo; the difference was considered statistically significant if the p-value was less than 0.05.

The percentage of days with neither daytime nor nighttime heartburn was calculated for each subject who has at least 1 daytime or nighttime heartburn result (presence or absence of heartburn) during the 4 weeks of treatment (up to last dose day or Day 35 whichever is first) by calculating:

$$\text{Percentage of days with neither daytime nor nighttime heartburn} = \frac{\text{(the days that were heartburn-free during Treatment Period)}}{\text{(Total number of days for which either a daytime or nighttime result was marked during Treatment Period)}} \times 100\%;$$

all entries on a day must be heartburn-free in order for the day to be counted as a day with neither daytime nor nighttime heartburn.

The days with missing diary results for both daytime and nighttime were excluded from the numerator and denominator. If a subject prematurely terminated, the Treatment Period was defined as from first dose date to last dose date + 1 day. If last dose date was missing, then 35 days was imputed as treatment period.

Subgroup Analyses:

Similar descriptive statistics and Wilcoxon rank-sum tests were repeated on the primary endpoint to evaluate the treatment effect within the different baseline subpopulation levels as follows:

- Age (<45, ≥45 to <65, ≥65 years).
- Gender (male, female).
- BMI (<25, 25-<30, ≥30 kg/m²).
- *H pylori* status (positive, negative).
- Overall study drug compliance (<80%, 80-<90%, ≥90%).

Ad Hoc Sensitivity Analysis

Similar descriptive statistics and two sample T-test were repeated on the primary endpoint to evaluate the treatment effect.

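### When the last-dose date is missing and drug is unreturned, SAP 5.9 credits a subject lost before Week 2 with 35 capsules out of 21 dispensed and scores 100% compliance

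*SAP*

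**What the plan says.** SAP 5.9 defines overall study-drug compliance as "total count of capsules taken / total number of days on study drug", times 100%. Exposure is last dose date minus first dose date plus 1. Three conventions follow in the same section:

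- Missing last-dose date: "If last dose date was missing, then 35 days were imputed as treatment period".
- Unreturned drug: "Subjects with unreturned study drug were assumed to have taken 1 capsule of study drug for each day of exposure".
- Cap: "Subjects with overall compliance ≥100% were set to 100% in the analysis". The cap acts on the percentage. Nothing limits the capsules credited to the number dispensed.

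SAP 5.10.1 repeats the 35-day rule for the primary endpoint's treatment period: "If last dose date was missing, then 35 days was imputed as treatment period". It also makes compliance class (<80%, 80-<90%, ≥90%) a subgroup factor for that endpoint.

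SAP 5.2.3 states a general rule: "Completely missing start or end dates remained missing, with no imputation applied". SAP 5.2.2 says that nothing is imputed apart from missing or partial dates under 5.2.3.

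On supply, Protocol 8.1.3 says "Subjects will receive three 7-day cards on Study Day -1 and Week 2", and Protocol 8.1.1 says the drug is "packaged in 7-day child resistant blister cards containing 7 OE capsules".

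**The concern.** Each convention looks harmless alone. Together they act on the subjects about whom least is known. Someone lost to follow-up may well have neither a recorded last dose nor returned blister cards. For that person the rules assign 35 days of exposure, which is longer than the planned four weeks, and full compliance. If the loss came before the second dispensing, the credited intake is more than the subject could have held. The same 35 days enlarges the denominator of diary compliance, so one record is scored fully compliant with drug and poorly compliant with the diary.

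The consequence that matters most is classification. The primary analysis gave p = 0.057. SAP 9.1 then relies on the ≥90% compliance subgroup (p = 0.037, Table 7.b) to argue that the drug works when taken consistently. A rule that places subjects of unknown intake in that class weakens what the class is meant to represent.

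**Working it through.** **Reported figure reproduced.** Table 7.b puts 106 placebo and 103 dexlansoprazole subjects in the ≥90% class. (106 + 103)/215 = 97.2%, which agrees with the ≥97% stated in SAP 9.1.

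**Worked record.** The subject takes drug on Days 1 to 7, completes the diary on those days, is lost before Week 2, returns nothing and has no last-dose date.

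- Dispensed on Day -1: 3 cards × 7 = 21 capsules (Protocol 8.1.1, 8.1.3), assuming no replacement supply under Protocol 8.2.
- Exposure under 5.9: 35 days. Overstatement: 35 − 7 = 28 days.
- Capsules credited: 1 × 35 = 35, which is 35 − 21 = 14 more than were dispensed.
- Compliance: 35/35 = 100%, so the ≥90% class.
- With capsules capped at 21 and the 35 days kept: at most 21/35 = 60%, so the <80% class.
- Diary compliance: 7/35 = 20%. If the last drug day is left out as in SAP 5.2.5, 7/34 = 20.6%.

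Both conditions are needed. After the Week 2 dispensing the subject has received 42 capsules, and 35 is no longer impossible.

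**Effect on arm means, per affected subject (n = 107 or 108).**

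| True last dose | Exposure overstated | Shift in arm mean |
|---|---|---|
| Day 1 | 34 days | 0.31–0.32 day |
| Day 7 | 28 days | 0.26 day |
| Day 13 | 22 days | 0.20–0.21 day |

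The reported mean is 26.8 days in each arm. For the Day 7 stop, mean diary compliance falls by (100 − 20)/107 = 0.75 point.

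**How many subjects.** The documents do not say. If every completer has a last-dose date, the range is 0 to 10, the early discontinuations in Table 6.a (6 placebo, 4 dexlansoprazole). The extreme case, with all of them affected and all stopping on Day 1, is 6 × 34/108 = 1.9 days for placebo and 4 × 34/107 = 1.3 days for dexlansoprazole. Two subjects per arm stopped for adverse events and probably have a stop date. That leaves 4 and 2. With Day 7 stops, the shifts are 4 × 28/108 = 1.04 and 2 × 28/107 = 0.52 day.

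**Sensitivity of the ≥90% subgroup to one record.** Table 7.b classifies 0 + 1 + 106 = 107 of 108 placebo subjects and 1 + 3 + 103 = 107 of 107 on dexlansoprazole. One placebo subject has no class. That subject's primary score follows from the reported means: 108 × 36.98 − 106 × 35.95 − 83.33 = 99.8% (98.7 to 100 after rounding).

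The effect of adding this subject to the ≥90% class can be approximated with the normal form of the Wilcoxon test, without tie correction:

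- p = 0.037 gives z = 2.086. The standard deviation of the statistic is √(103 × 106 × 210/12) = 437.1, so its excess over expectation is 911.7.
- A placebo subject ranked above all 103 dexlansoprazole subjects lowers the excess by 103/2 = 51.5, to 860.2. The new standard deviation is √(103 × 107 × 211/12) = 440.2.
- z = 1.954, p = 0.051. If 15 dexlansoprazole subjects tie with this subject, the excess is 867.7, z = 1.971 and p = 0.049.

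So the class given to a single record can move the cited result to about 0.05. The documents do not say why this subject is unclassified. Nothing links the case to the 35-day rule.

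**The case against.** The case for leaving the rules alone has several sound parts.

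- A reader might infer that the primary endpoint is distorted. In the worked record it is not. SAP 5.10.1 counts only days with a marked daytime or nighttime result, so seven diary days give the same percentage whether the period is 7 or 35 days. A change needs diary entries after dosing stopped and still no last-dose date, which is not the typical lost subject.
- Day 35 is not arbitrary. It is the SAP's own outer limit: Table 5.a runs Week 4 to Day 35, and 5.2.5 ends diary summaries there at the latest. It does lie beyond the protocol's last permitted Week 4 visit (28 + 3 = Day 31).
- A reader might call 5.9 and 5.2.3 a flat contradiction. They can be read as a specific rule over a general one, because 5.9 leaves the date missing and assigns a duration. A cross-reference is missing, but the two can coexist.
- It is tempting to attribute the gap in diary compliance between arms (95.74 − 93.84 = 1.90 points) to two or three such subjects. At 0.75 point each, two give 1.50 and three about 2.24, but only if all are on dexlansoprazole. Affected placebo subjects would narrow the gap. The documents give no counts.
- Equal mean exposure in the two arms shows no sign of a problem, and the unclassified placebo subject shows that incomplete data did not always end in the ≥90% class.

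These points limit the reach of the concern. They do not answer the arithmetic: as written, 5.9 can credit more capsules than were dispensed and label the subject fully compliant.

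**Conclusion.** The point holds as a defect in the exposure and compliance rules of SAP 5.9. For a subject lost before Week 2 with no last-dose date and unreturned drug, the rules give 35 capsules against 21 dispensed and 100% compliance. With a Day 7 stop, exposure is 28 days too long, about 0.26 day on an arm mean per subject, and diary compliance is about 20%. The subject also enters the ≥90% subgroup used to interpret the primary endpoint.

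The size rests on two assumptions: no replacement supply, and a number affected between 0 and 10, which the documents do not report and which may be zero. It would go too far to say that the rule produced the p-value of 0.037 or biased the primary analysis. No affected subject is identified. What the documents do support is that the subgroup result is sensitive to how a single record is classed, so the classification rule needs to be sound and its use reported. The change is worth making, but it does not alter the primary result.

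**What to change.** 1. In 5.9, when the last-dose date is missing, do not count unreturned capsules as taken. Set study-drug compliance to missing, or show low and high bounds with capsules capped at the number dispensed.
2. Leave such subjects out of the ≥90% class, or show the subgroup result with and without them.
3. In 5.9 and 5.10.1, replace the flat 35 days with an upper limit no later than the last known contact and the last day covered by dispensed capsules (Day 21 at one capsule a day, if lost before Week 2). Add a sensitivity summary that ends treatment at the last recorded evidence of dosing. The last diary entry should not serve as the only end point: if diary entry lapses while dosing goes on, that would cut exposure short and inflate diary compliance.
4. Reconcile these rules with 5.2.2 and 5.2.3 by cross-reference.
5. Report how many subjects each rule touched, by arm, and explain the placebo subject with no compliance class in Table 7.b.

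The cost is wording and a small amount of programming on data that should already be held. A few compliance values become missing or less favourable. The SAP text already reports unblinded results, so any reclassified subgroup result must be labelled post hoc and shown beside the reported one.

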5.10 Efficacy Analysis

The FAS was used for the summary of the efficacy endpoints.

5.10.1 Primary Efficacy Endpoint

The percentage of days with neither daytime nor nighttime heartburn over the 4 weeks of treatment was summarized descriptively. Comparisons between dexlansoprazole capsules and placebo was made using a Wilcoxon rank-sum test. The two-sided p-value was presented for the difference between dexlansoprazole capsules and placebo; the difference was considered statistically significant if the p-value was less than 0.05.

The percentage of days with neither daytime nor nighttime heartburn was calculated for each subject who has at least 1 daytime or nighttime heartburn result (presence or absence of heartburn) during the 4 weeks of treatment (up to last dose day or Day 35 whichever is first) by calculating:

$$\text{Percentage of days with neither daytime nor nighttime heartburn} = \frac{\text{(the days that were heartburn-free during Treatment Period)}}{\text{(Total number of days for which either a daytime or nighttime result was marked during Treatment Period)}} \times 100\%;$$

all entries on a day must be heartburn-free in order for the day to be counted as a day with neither daytime nor nighttime heartburn.

The days with missing diary results for both daytime and nighttime were excluded from the numerator and denominator. If a subject prematurely terminated, the Treatment Period was defined as from first dose date to last dose date + 1 day. If last dose date was missing, then 35 days was imputed as treatment period.

Subgroup Analyses:

Similar descriptive statistics and Wilcoxon rank-sum tests were repeated on the primary endpoint to evaluate the treatment effect within the different baseline subpopulation levels as follows:

- Age (<45, ≥45 to <65, ≥65 years).
- Gender (male, female).
- BMI (<25, 25-<30, ≥30 kg/m²).
- *H pylori* status (positive, negative).
- Overall study drug compliance (<80%, 80-<90%, ≥90%).

Ad Hoc Sensitivity Analysis

Similar descriptive statistics and two sample T-test were repeated on the primary endpoint to evaluate the treatment effect.

5.10.2 Secondary Efficacy Endpoints

Descriptive statistics (mean, median, standard deviation, minimum and maximum) were presented similarly to the primary endpoint. Comparisons between dexlansoprazole capsules and placebo was made using a Wilcoxon rank-sum test. The p-value was presented for the difference between dexlansoprazole capsules and placebo; the difference was considered significant if the two-sided p-value was less than 0.05. The ad hoc sensitivity analysis described for the primary endpoint was also performed on the secondary endpoint.

5.10.3 Additional Efficacy Endpoints

The severity of GERD symptoms at Weeks 2 and 4 was analyzed using a Cochran-Mantel-Haenszel (CMH) test for ordered responses with baseline severity as the stratum. The p value was presented for the difference between dexlansoprazole capsules and placebo; the difference was considered significant if the p-value was less than 0.05.

The percentage of days without rescue medication over 4 weeks as assessed by daily eDiary was analyzed using the Wilcoxon rank-sum test.

In addition, descriptive statistics were presented for the endpoints below:

- The percentage of days without daytime heartburn over the 4 weeks of treatment as assessed by daily eDiary.
- The severity of daytime and nighttime heartburn hurt over the 4 weeks of treatment as assessed by daily eDiary.
- The severity of nighttime heartburn hurt over the 4 weeks of treatment as assessed by daily eDiary.
- The severity of daytime heartburn hurt over the 4 weeks of treatment as assessed by daily eDiary.

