All subjects returned to the investigative site on Day -1, which was deemed as the Baseline. Subjects who had completed all of the Screening procedures and met all eligibility requirements and none of the exclusion criteria had routine fasting laboratory evaluations including fasting serum gastrin, a urine pregnancy test (all women subjects of childbearing potential), a physical examination and vital signs measurements to assure continued eligibility. In addition, subjects were assessed by the investigator for GERD symptoms such as heartburn, acid regurgitation, dysphagia, belching, and epigastric pain.

Subjects were dispensed study drug on Day -1 according to an Interactive Web Response System (IWRS) and began taking study drug on the following day (Day 1). Rescue medication continued to be supplied during the Treatment Period.

Subjects were randomized in a 1:1 ratio to one of the following 2 treatment groups during the 4-week Treatment Period:

Group I: dexlansoprazole capsules (30 mg QD)

[figure not shown]
Group II: placebo (QD)

During this 4-week Treatment Period, study drug was self-administered, orally, once a day, in the morning, without regard to food. Subjects continued to document the presence and maximum

severity of daytime and nighttime heartburn symptoms and record usage of rescue medication using an eDiary. Subject visits were conducted at Weeks 2 and 4 of the Treatment Period to collect and/or dispense study drug, assess GERD symptoms, review concomitant medication use, assess adverse events, and perform a physical examination including vital signs. In addition, at the Week 4/ Final Visit, all subjects underwent laboratory evaluations, ECG, fasting serum gastrin and urine pregnancy test (all women of childbearing potential). Subjects who prematurely discontinued after randomization underwent Week 4/Final Visit procedures no later than 5 days after the last dose of study drug.

A schematic of the study design is included as [Figure 2.a](#).

Figure 2.a Schematic of Study Design

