7.1 Primary and Secondary Efficacy Endpoint

The median percentage of days with neither daytime nor nighttime heartburn for subjects in the dexlansoprazole capsules group (51.72%) was greater than for subjects in the placebo group (32.67%) with the difference of 19.05%. The difference between treatment groups was not statistically significant ($P=0.057$) (Table 7.a).

Subgroup analyses were performed on the primary endpoint, and these results are presented in Table 7.b. For subjects with positive *H pylori* results, the median percentage of days with neither daytime nor nighttime heartburn for subjects in the dexlansoprazole capsules group (68.62%) was greater than for those in the placebo group (34.62%), and the difference (34.00%) was statistically significant with $p\text{-value} = 0.032$. For subjects with the highest overall study drug compliance ($\geq 90\%$), the median in the dexlansoprazole capsules group (51.72%) was also greater than for those in the placebo group (30.29%), and the difference (21.43%) was statistically significant with $p\text{-value} = 0.037$.

For the secondary endpoint of percentage of days without nighttime heartburn over 4 weeks, the median value of dexlansoprazole capsules group (67.86%) was greater compared with placebo group (54.67%). The difference (13.19%) between treatment groups was not statistically significant ($P=0.268$) (Table 7.a).

For the percentage of days without daytime heartburn over 4 weeks, the median value of dexlansoprazole capsules group (62.96%) was greater compared with placebo group (46.55%) (Table 7.a).

An ad hoc sensitivity analysis was performed on the primary and secondary efficacy endpoints.. For primary efficacy endpoint, the difference between treatment groups was statistically significant ($P=0.029$) (Table 15.2.6). For the secondary efficacy endpoint, the difference between the treatment groups was not statistically significant ($P=0.365$) (Table 15.2.7).

Table 7.a Percentage of Days Without Heartburn During Treatment (Full Analysis Set)

	Placebo QD N = 108	Dexlansoprazole 30 mg QD N = 107
Primary endpoint: percentage of days with neither daytime nor nighttime heartburn during treatment ^a		
N	108	107
Mean (SD)	36.98 (31.999)	47.21 (35.995)
Median	32.67	51.72
P-value ^b		0.057
Secondary endpoint: percentage of days without nighttime heartburn during treatment		
N	108	107
Mean (SD)	50.38 (34.309)	54.83 (37.449)
Median	54.67	67.86
P-value ^b		0.268

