9.2 Conclusion

In this 4-week study of dexlansoprazole 30 mg or placebo in Chinese subjects with symptomatic nonerosive GERD, dexlansoprazole was safe and well tolerated. Subjects taking dexlansoprazole had a greater percentage of days without daytime or nighttime heartburn (difference of 19 percentage points) and without nighttime heartburn alone (difference of 13 percentage points) than subjects taking placebo, but the differences between the treatment groups were not statistically significant. Statistically significant improvements were observed, however, in several investigator-assessed GERD symptoms after 4 weeks of treatment with dexlansoprazole (an additional endpoint). In addition, subjects taking dexlansoprazole used statistically significantly less rescue medication than those taking placebo.

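### The additional-endpoint tests (ten symptom tests and rescue-free days) have no familywise error control, yet after the primary failed the report calls five of them statistically significant without marking them nominal

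*SAP*

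**What the plan says.** The SAP document (a past-tense report dated 07 December 2018) sets a separate 0.05 rule at each level of endpoint:

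- Primary, 5.10.1: "the difference was considered statistically significant if the p-value was less than 0.05".
- Secondary, 5.10.2: "the difference was considered significant if the two-sided p-value was less than 0.05".
- Symptom severity, 5.10.3: "The severity of GERD symptoms at Weeks 2 and 4 was analyzed using a Cochran-Mantel-Haenszel (CMH) test", followed by "the difference was considered significant if the p-value was less than 0.05". Section 2.0 names the symptoms as "heartburn, acid regurgitation, dysphagia, belching, and epigastric pain".
- Rescue use, 5.10.3: "The percentage of days without rescue medication over 4 weeks as assessed by daily eDiary was analyzed using the Wilcoxon rank-sum test". No significance threshold follows.

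None of these rules depends on another. SAP section 5 and protocol section 13 contain no hierarchy, gate, alpha split or adjustment.

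Sections 7.1 and 9.2 report the primary (p = 0.057) and the secondary (p = 0.268) as not significant. Section 9.2 then goes on: "Statistically significant improvements were observed, however, in several investigator-assessed GERD symptoms after 4 weeks of treatment". It adds that rescue use was also significantly lower on dexlansoprazole. The synopsis carries the same text, 7.3 and 9.1 make the same two claims, and 7.2.2 makes the rescue claim.

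**The concern.** When each of a dozen tests is read alone at 0.05, the chance that at least one crosses the line by luck is well above 5%. That does little harm if the p-values are presented as descriptive. Here they are not. Once the primary and secondary had failed, the only efficacy results called significant in the conclusion were additional-endpoint tests, and the sentence that introduces them sets them against the failed primary. The word *significant* is the same one used for the controlled primary test, so a reader has no signal that its meaning has changed.

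At stake is what the trial may be said to have shown. Section 9.2 speaks of several symptoms; only 9.1 tells the reader that dysphagia and epigastric pain showed no significant difference.

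**Working it through.** **The plan's own figure.** The documents give no familywise error rate. Their one design calculation (SAP 4.0, protocol 13.3) concerns the primary alone: 80 per arm, difference 25, SD 35, two-sided 0.05. The standard error is 35 × √(2/80) = 5.53. Then 25/5.53 = 4.52 and 4.52 − 1.96 = 2.56, which gives power of about 0.995. The stated figure of at least 95% is met. The calculation allots nothing to later endpoints.

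**Number of tests.** 5 symptoms (SAP 2.0) × 2 visits (5.10.3) = 10. Adding rescue-free days gives 11 additional tests, and adding the secondary gives 12. Subgroup tests and the post-unblinding t-tests are left out.

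**Reported p-values.** From 9.1: heartburn 0.009 (Week 2) and 0.005 (Week 4); acid regurgitation 0.008 and belching 0.042 (both Week 4). From 7.2.2: rescue 0.009. The other six symptom p-values are not given in 9.1. I take them to exceed 0.05, since none is reported as significant.

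**Chance of at least one false positive under a global null.** With independent tests this is 1 − 0.95^k:

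- k = 11: 1 − 0.95^11 = 0.431
- k = 12: 1 − 0.95^12 = 0.460

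The tests share subjects, symptoms and visits, so they are correlated, but the documents give no correlation. Simulating equally correlated normal statistics, two-sided at 0.05, gives:

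| Assumed correlation | 11 tests | 12 tests |
|---|---|---|
| 0.3 | 38% | 40% |
| 0.5 | 30% | 32% |
| 0.7 | 22% | 23% |
| 0.9 | 13% | 13% |

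The value falls to 5% only at perfect correlation. The Bonferroni upper bound for 12 tests is 12 × 0.05 = 60%.

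**Holm-adjusted p-values.** The ordered p-values are multiplied by m, m − 1, and so on, and each adjusted value is at least as large as the one before it.

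| Family | m | 0.005 | 0.008 | 0.009 | 0.009 | 0.042 |
|---|---|---|---|---|---|---|
| Additional tests | 11 | 0.055 | 0.080 | 0.081 | 0.081 | 0.294 |
| Additional + secondary | 12 | 0.060 | 0.088 | 0.090 | 0.090 | 0.336 |
| Ten symptom tests | 10 | 0.050 | 0.072 | 0.072 | not in family | 0.294 |
| Week 4 symptoms + rescue (post hoc) | 6 | 0.030 | 0.040 | 0.040 | not in family | 0.126 |

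**Rounding.** A p printed as 0.005 lies between 0.0045 and 0.0055. Multiplied by 10 it spans 0.045 to 0.055, so the ten-test result is undetermined. Multiplied by 11 it spans 0.0495 to 0.0605; only a true p from 0.0045 to about 0.00454 would pass. Multiplied by 12 it spans 0.054 to 0.066, and cannot pass.

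**The case against.** The strongest defence is that the tiers were fixed in the protocol, the confirmatory claim rests on one primary test, there is no interim analysis, and the report says plainly that the primary and secondary missed. Section 9.2 even tags the symptom result as an additional endpoint, and 7.3 ties the failure to the pre-planned analysis. All of this is true. A reader might infer that the trial has no error control, or that the failure is concealed. Neither is supported: the primary keeps its two-sided 5% level and its failure is disclosed.

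A reader might also infer that the secondary was wrongly called significant. It was not. It had its own 0.05 rule, but it was reported as negative and no claim was built on it.

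Nor do the documents support saying that no alpha was left. That presumes a fixed sequence which they never set. What they lack is any rule at all beyond the primary.

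Lastly, the adjusted outcome depends on the family. For the five Week 4 symptoms plus rescue, Holm keeps heartburn, acid regurgitation and rescue, and drops only belching. That is a fair warning against saying that nothing could survive. But no document defines that family, and choosing it with the results in hand is post hoc.

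What remains is narrower: the endpoint label is present, but the p-values are nowhere marked nominal, unadjusted or exploratory.

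**Conclusion.** The point holds for the additional endpoints. Their p-values have no familywise control and no link to the primary result, and the rescue result is called significant although 5.10.3 gives that test no threshold. Under a global null, the chance of at least one false positive among 12 tests is about 46% if they are independent, and about 40% to 13% at assumed equal correlations of 0.3 to 0.9. At the reported precision none of the five nominal findings passes Holm over 11 or 12 tests. Over the ten symptom tests alone, Week 4 heartburn cannot be decided.

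It would be tempting to conclude that the symptom and rescue findings are false positives. The figures do not show that. Five or more nominal hits in 11 independent null tests would have probability of about 0.0001; correlation would raise that figure by an amount the documents do not allow one to compute. The findings are unconfirmed, not refuted. The primary analysis and its reported failure are unaffected.

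**What to change.** In 5.10.3, 7.2.2, 7.3, 9.1, 9.2 and the synopsis, label every additional-endpoint p-value *nominal, not adjusted for multiplicity; exploratory because the primary endpoint was not met*, and remove the significance wording for the symptom and rescue results. In 5.10.3 also record that no threshold was stated for the rescue test. Section 9.2 could read: *Nominal p-values below 0.05, unadjusted for multiplicity, were seen for investigator-assessed heartburn, acid regurgitation and belching at Week 4 and for rescue-free days; these are exploratory because the primary endpoint was not met.*

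Do not add a test order to 5.10 as if it had been pre-specified. The results are known, so it cannot restore error control. If adjusted p-values are shown, state the family and mark them as supportive only.

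The change needs no new data. The amendment appendix already records a similar correction, which took the ad hoc analyses out of the main efficacy table to make clear what had been planned. The cost is report wording and a less favourable conclusion.
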